13.1. Statistical Analysis Report

The TLF (Tables, Listings and Figures) will follow the list of tables, plots, and listings agreed with the Study Physician. The SAR will follow the list of tables, plots, and listings listed in the following section. The index is intended to provide the overall idea of the general output and ordering of the SAR, it will not necessarily be reproduced in the SAR.

13.2. Index of TLFs

13.2.1. Tables

Baseline Tables

Table 1.1: Patients Disposition
Table 1.2: Reason for discontinuation
Table 1.3: Demographics and Baseline Characteristics
Table 1.4: AML specific Medical History
Table 1.5: Mutation status
Table 1.6: Medical History by System Organ Class and Preferred Term
Table 1.7: Concomitant Medication by ATC Code
Table 1.8: Prior Medication for Cancer other than AML by ATC Code
Table 1.9: Prior Medication (Leukemia only) by ATC Code
Table 1.10: Number of Previous Treatments for Leukemia
Table 1.11: Drug Modification by Cycle
Table 1.12: Procedures by System Organ Class and Preferred Term

Safety Tables

Table 2.1 Adverse Events Summary
Table 2.1.1: Adverse Events by System Organ Class and Preferred Term
Table 2.1.2: Adverse Events by Grade, System Organ Class and Preferred Term
Table 2.1.2.1: Adverse Events by Grade, System Organ Class and Preferred Term (Grade < 3)
Table 2.1.2.2: Adverse Events by Grade, System Organ Class and Preferred Term (Grade \geq 3)
Table 2.1.3: Adverse Events leading to Drug Withdrawn by System Organ Class and Preferred Term
Table 2.1.4: Adverse Events leading to Drug Interruption by System Organ Class and Preferred Term
Table 2.1.5: Adverse Events leading to Drug Reduction by System Organ Class and Preferred Term
Table 2.2.1: Related Adverse Events by System Organ Class and Preferred Term
Table 2.2.2: Related Adverse Events by Grade, System Organ Class and Preferred Term
Table 2.2.2.1: Related Adverse Events by Grade, System Organ Class and Preferred Term (Grade < 3)
Table 2.2.2.2: Related Adverse Events by Grade, System Organ Class and Preferred Term (Grade \geq 3)
Table 2.2.3: Related Adverse Events leading to Drug Withdrawn by System Organ Class and Preferred Term
Table 2.2.4: Related Adverse Events leading to Drug Interruption by System Organ Class and Preferred Term
Table 2.2.5: Related Adverse Events leading to Drug Reduction by System Organ Class and Preferred Term

Table 2.3.1: Serious Adverse Events by System Organ Class and Preferred Term
 Table 2.3.2: Serious Adverse Events by Grade, System Organ Class and Preferred Term
 Table 2.3.2.1: Serious Adverse Events by Grade, System Organ Class and Preferred Term (Grade < 3)
 Table 2.3.2.2: Serious Adverse Events by Grade, System Organ Class and Preferred Term (Grade ≥ 3)
 Table 2.3.3: Serious Adverse Events leading to Drug Withdrawn by System Organ Class and Preferred Term
 Table 2.3.4: Serious Adverse Events leading to Drug Interruption by System Organ Class and Preferred Term
 Table 2.3.5: Serious Adverse Events leading to Drug Reduction by System Organ Class and Preferred Term
 Table 2.4.1: Serious and Related Adverse Events by System Organ Class and Preferred Term
 Table 2.4.2: Serious and Related Adverse Events by Grade, System Organ Class and Preferred Term
 Table 2.4.3: Serious and Related Adverse Events leading to Drug Withdrawn by System Organ Class and Preferred Term
 Table 2.4.4: Serious and Related Adverse Events leading to Drug Interruption by System Organ Class and Preferred Term
 Table 2.4.5: Serious and Related Adverse Events leading to Drug Reduction by System Organ Class and Preferred Term
 Table 2.5.1: Dose Limiting Toxicity by System Organ Class and Preferred Term
 Table 2.5.2: Adverse Events leading to Death by System Organ Class and Preferred Term
 Table 2.5.3: Related Adverse Events leading to Death by System Organ Class and Preferred Term
 Table 2.6: Overall summary of Haematology Laboratory Parameters by Visit
 Table 2.6.1: Change vs Baseline of Haematology Laboratory Parameters by Visit
 Table 2.6.2: Shift Table for Haematology Laboratory Parameters
 Table 2.7: Overall summary of Clinical Chemistry Laboratory Parameters by Visit
 Table 2.7.1: Change vs Baseline of Clinical Chemistry Laboratory Parameters by Visit
 Table 2.7.2: Shift Table for Clinical Chemistry Laboratory Parameters
 Table 2.8: Overall summary of Coagulation Laboratory Parameters by Visit
 Table 2.8.1: Change vs Baseline of Coagulation Laboratory Parameters by Visit
 Table 2.9: Overall summary of Lipid Panel Parameters by Visit
 Table 2.9.1: Change vs Baseline of Lipid Panel Parameters by Visit
 Table 2.10: Overall summary of Bone Marrow Laboratory Parameters by Visit
 Table 2.11.1: Change vs Baseline of Bone Marrow Laboratory Parameters by Visit
 Table 2.12: Overall summary of Urinalysis Laboratory Parameters by Visit (Categorical Variables)
 Table 2.12.1: Overall summary of Urinalysis Laboratory Parameters by Visit (Continuous Variables)
 Table 2.13: Overall summary of Echocardiogram by Visit
 Table 2.14: Overall summary of ECG by Visit
 Table 2.14.1: Change vs Baseline of ECG by Visit
 Table 2.15: Overall summary of ECOG Performance Status by Visit
 Table 2.16: Overall summary of Physical Examination Parameters by Visit
 Table 2.17: Overall summary of Vital Signs by Visit

Efficacy Tables (to be performed on both efficacy population as well as safety population)

Table 3.1: Summary of Tumor Response by Visit
 Table 3.2: Summary of Tumor Response Endpoints
 Table 3.3: Summary of Time to Event Endpoints

PK Tables

Table 4.1: Summary statistics of MEN1703 PK concentration in plasma by cohort, cycle, day, IDH mutational status and nominal time point, and by dose, cycle, day, IDH mutational status and nominal time point
 Table 4.2: Summary statistics of MEN1703 PK parameters by cohort, cycle, day, IDH mutational status and nominal time point, and by dose, cycle, day, IDH mutational status and nominal time point.
 Table 4.3: Summary statistics of MEN1703 PK concentration in urine by cohort, cycle, day, IDH mutational status and nominal time point, and by dose, cycle, day, IDH mutational status and nominal time point
 Table 4.4: Summary statistics of MEN1703 urinary PK parameters by cohort, cycle, day, IDH mutational status and nominal time point, and by dose, cycle, day, IDH mutational status and nominal time point
 Table 4.5: Summary statistics of MET3 PK concentration in plasma by cohort, cycle, day, IDH mutational status and nominal time point, and by dose, cycle, day, IDH mutational status and nominal time point
 Table 4.6: Summary statistics of MET3 PK parameters by cohort, cycle, day, IDH mutational status and nominal time point, and by dose, cycle, day, IDH mutational status and nominal time point.

Table 4.7: Summary statistics of MET3 PK concentration in urine by cohort, cycle, day, IDH mutational status and nominal time point, and by dose, cycle, day, IDH mutational status and nominal time point

Table 4.8: Summary statistics of MET3 urinary PK parameters by cohort, cycle, day, IDH mutational status and nominal time point, and by dose, cycle, day, IDH mutational status and nominal time point

13.2.2. Listings

Listings

- Listing 4.1: Demographic Characteristics
- Listing 4.2: Reason for discontinuation
- Listing 4.3: Tumor History Characteristics
- Listing 4.4: Tumor History Previous Treatment
- Listing 4.5: Medical History
- Listing 4.6: Previous Treatment
- Listing 4.7: Previous Procedure
- Listing 4.8: Concomitant Medication
- Listing 4.9 - 4.10: Adverse Event (Part 1 - Part 2)
- Listing 4.11: Adverse Events
- Listing 4.11.1: Adverse Events of Grade ≥ 3
- Listing 4.11.2: Serious Treatment Emergent Adverse Events
- Listing 4.11.3: Serious and Related Treatment Emergent Adverse Events
- Listing 4.11.4: Dose Limiting Toxicities
- Listing 4.11.5: Adverse Events leading to Drug Withdrawn
- Listing 4.11.6: Adverse Events leading to Drug Interruption
- Listing 4.11.7: Adverse Events leading to Drug Reduction
- Listing 4.11.8: Adverse Events leading to death
- Listing 4.12: Haematology
- Listing 4.13: Clinical Chemistry
- Listing 4.14: Coagulation
- Listing 4.14.1: Lipid panel
- Listing 4.15: Urinalysis
- Listing 4.16: Bone Marrow
- Listing 4.17: Electrocardiogram
- Listing 4.18: ECOG Performance Status
- Listing 4.19: Physical Examination
- Listing 4.20: Vital Signs
- Listing 4.21: Mutations
- Listing 4.22: Treatment Intake – SEL24/MEN1703
- Listing 4.23: Tumor Response by Timepoint
- Listing 4.24: individual MEN1703 plasma PK concentrations
- Listing 4.25: individual MEN1703 plasma PK parameters
- Listing 4.26: Individual MEN1703 urinary PK concentrations over 24-hours
- Listing 4.27: Individual MEN1703 urinary PK parameter
- Listing 4.28: individual MET3 plasma PK concentrations
- Listing 4.29: individual MET3 plasma PK parameters
- Listing 4.30: Individual MET3 urinary PK concentrations over 24-hours
- Listing 4.31: Individual MET3 urinary PK parameter

13.2.3. Figures

Figures

- Figure 1: Overall Mean and Median timecourse – ALT ($\mu\text{kat/L}$)
- Figure 2: Overall Mean and Median timecourse – AST ($\mu\text{kat/L}$)
- Figure 3: Overall Mean and Median timecourse – Blasts ($10^9/\text{L}$)
- Figure 4: Overall Mean and Median timecourse – Hemoglobin (g/L)
- Figure 5: Overall Mean and Median timecourse – Lymphocytes ($10^9/\text{L}$)

Figure 6: Overall Mean and Median timecourse – Neutrophils ($10^9/L$)
Figure 7: Overall Mean and Median timecourse – Platelet ($10^9/L$)
Figure 8: Overall Mean and Median timecourse – White Blood Cells ($10^9/L$)
Figure 9: Overall Mean and Median timecourse – Total Bilirubin ($\mu mol/L$)
Figure 10: Overall Mean and Median timecourse – Direct Bilirubin ($\mu mol/L$)
Figure 11: Overall timecourse – ALT ($\mu kat/L$)
Figure 12: Overall timecourse – AST ($\mu kat/L$)
Figure 13: Overall timecourse – Blasts ($10^9/L$)
Figure 14: Overall timecourse – Hemoglobin (g/L)
Figure 15: Overall timecourse – Lymphocytes ($10^9/L$)
Figure 16: Overall timecourse – Neutrophils ($10^9/L$)
Figure 17: Overall timecourse – Platelet ($10^9/L$)
Figure 18: Overall timecourse – White Blood Cells ($10^9/L$)
Figure 19: Overall timecourse – Total Bilirubin ($\mu mol/L$)
Figure 20: Overall timecourse – Direct Bilirubin ($\mu mol/L$)
Figure 21: Individual MEN1703 PK concentration-time profiles (separate)
Figure 22: MEN1703 PK concentration-time profiles (mean values with error bars)
Figure 23: Boxplots of MEN1703 C_{max} and AUC_{24} at Cycle 1 Day 1 and at Cycle 1 Day 14, versus dose
Figure 24: Individual MET3 PK concentration-time profiles (separate)
Figure 25: MET3 PK concentration-time profiles (mean values with error bars)
Figure 26: Boxplots of MET3 C_{max} and AUC_{24} at Cycle 1 Day 1 and at Cycle 1 Day 14, versus dose

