### 1.5. Safety Guidance Information for Investigators

Throughout the study, Investigators should refer to the current edition of the Investigator's Brochure (IB) for a full review of the potential risks associated with treatment with SEL24/MEN1703 and details of expected AEs.

Based on available safety data, administration of SEL24/MEN1703 may be associated with the potential risk of **fatal thrombosis** and **severe hepatotoxicity**. In addition, hypophosphatemia has occurred at the 25, 50, 75, and 150 mg dose levels. Please refer to [Section 6.9.1](#) for further guidance on the management of this latter event.

No other particular risks have been identified for SEL24/MEN1703 according to available clinical data. Nevertheless, results from non-clinical data do not allow to exclude the potential phototoxic effect of MEN1703. To this end, new safety measures - Inclusion of photosensitivity/phototoxicity

preventive measures – have been implemented in previous Clinical Trial Protocol Versions 11.2 and 11.3. Please refer to [Section 6.8](#) for further guidance on the prevention and management of this event.

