### 5.3.6. Clinical chemistry, hematology, coagulation, lipid profile and urinalysis

Blood and urine samples for determination of clinical chemistry, hematology, coagulation, lipid profile and urinalysis parameters will be taken at the times given in the Schedule of Study Assessment (Table 5). The date and time of collection will be recorded in the source data and on the CRF.

All testing will be performed at each site's local laboratory. Patients should be asked to follow local guidance for fasting prior to the lipid profile assessment. At time points where coagulation testing is performed, these parameters may be assessed from the hematology sample. Should a patient develop coagulation abnormalities at any point during the study, a comprehensive evaluation of coagulation abnormalities will be immediately performed which may include, but not be limited to repeat PT/INR, APTT, fibrinogen, D-dimer, plus a peripheral blood smear, thrombin time. These abnormalities have to be evaluated by the Investigator in conjunction with the patient's medical history, physical examination and concomitant medication review. Repeat testing may be performed as clinically indicated, which may include additional parameters or time-points. Additional tests will be performed as required to rule out other etiologies.

Copies of laboratory accreditation certificates and reference ranges will be obtained from each study site prior to the analysis of their first patient sample.

The laboratory variables to be measured are described in [Appendix E](#).

Results from the hematology test panel will contribute to each patient's disease assessment (see [Section 5.3.11](#)).

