11.5. Safety analysis

Safety and tolerability assessments will be evaluated on the safety population by means of descriptive statistics. Summary statistics (counts / (%) | number of events) will report the incidence of AEs using combinations of these variables for the descriptive statistics stratification: CTCAE toxicity grade, relationship with study drug, seriousness, System Organ Class or Body System, Preferred Term.

AEs summary tables will be created by Cohort (dose level) and Overall.

Counts and percentages will be produced for the results of the ECG, laboratory values (clinical chemistry, haematology, coagulation, bone marrow and urinalysis), vital signs, physical examination, classified as Normal/Abnormal NCS/Abnormal CS by Cohort (dose level) and Overall, stratified by Visit and timepoint – if applicable.

For ECG and hematology, clinical chemistry, coagulation and bone marrow laboratory data, the change from baseline will be summarized for each post baseline visit with descriptive statistics by cohort. For hematology and clinical chemistry laboratory parameters shift tables will be presented with the counts of individual shifts from each of the reference range categories from baseline to the worst post-baseline value by laboratory parameter by cohort and dose level.

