11.5.6. Safety laboratory tests

An overall summary table of clinical chemistry, haematology, coagulation, lipid profile, bone marrow and urinalysis parameters by Visit, cohort, dose and time-point will be provided in the TLFs. The change from baseline will be summarized for each post baseline visit with descriptive statistics by cohort.

12. Efficacy evaluations

Disease assessment will involve evaluation of leukemic blast proportion in the bone marrow.

Hematologic parameters from the routine local assessments including blast percentage (where applicable), absolute neutrophil count (ANC), platelet count, and other relevant parameters such as transfusion dependence will also contribute to this assessment. Evaluation of disease status will be performed at the time-points described in the Schedule of Study Assessment (Table 5). To note, disease assessment must be performed as soon as the peripheral lab results become consistent with an objective response. Disease assessment will also include an aliquot of bone marrow aspirate/biopsy that will be centrally stored for future analysis (e.g. minimal residual disease), if any.

In case bone marrow aspirate/biopsy is consistent with CRi or better response, but still a minimal percentage of peripheral blasts is detected, the response assessment can be postponed up to 2 weeks and will be based on repeated peripheral blood results and last bone marrow aspiration results.

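### Severe hepatotoxicity is a named risk, yet no planned output shows transaminase and bilirubin elevation together in one patient, or any liver test in multiples of the local upper limit of normal

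*SAP*

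**What the plan says.** Protocol 1.5 states that the drug "may be associated with the potential risk of fatal thrombosis and severe hepatotoxicity". Protocol 5.3.6 says "All testing will be performed at each site's local laboratory" and provides for each site's reference ranges to be obtained. Entry criterion 6 (Protocol 3.1) is written in multiples of ULN: AST and ALT up to 2.5x, total bilirubin up to 2x.

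The SAP plans these liver outputs:

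- **Curves (13.2.3).** Figures 1, 2, 9 and 10 are overall mean and median curves for ALT, AST, total and direct bilirubin, in µkat/L or µmol/L, for example "Figure 1: Overall Mean and Median timecourse – ALT" and "Figure 9: Overall Mean and Median timecourse – Total Bilirubin". A second set (Figures 11, 12, 19 and 20) is titled in the style of "Figure 11: Overall timecourse – ALT", with no statement of what is drawn.
- **Tables by visit (11.2, 11.5.6).** Summaries are by visit, cohort, dose and time-point, with minimum and maximum among the statistics. In addition, "The change from baseline will be summarized for each post baseline visit with descriptive statistics by cohort".
- **Shift tables (11.5; Table 2.7.2).** These count shifts between reference-range categories "from baseline to the worst post-baseline value by laboratory parameter by cohort and dose level". The categories are not defined.
- **Counts of normal, abnormal not clinically significant and abnormal clinically significant results (11.5)**, by cohort and overall.
- **Patient-level listings (13.2.2).** Listing 4.13 gives chemistry, 4.11.1 adverse events of Grade 3 or higher, and 4.11.4 dose-limiting toxicities.

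**The concern.** Severe liver injury, if it occurs, occurs in individual patients. A reader of the report will want to know how high each patient's transaminases went relative to that laboratory's limit, and whether bilirubin rose in the same patient. The planned outputs do not answer either question directly. Curves of pooled averages are insensitive to single patients. Absolute units mix laboratories whose upper limits may differ, although the protocol itself works in multiples of ULN at entry and, through Protocol 4.4, for re-treatment. Tables that take one test at a time cannot separate an isolated transaminase rise from a rise in both tests.

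Safety laboratory results are part of the Part 2 primary endpoint (SAP 5.4.1), so the gap lies in the main analysis of that part.

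**Working it through.** **Denominator.** SAP Table 1 gives the Part 1 cohorts as 2 + 3 + 3 + 3 + 3 + 7 + 3 + 1 = 25. Adding the two planned expansion cohorts, 25 + 20 + 20 = 65, which reproduces the approximately 65 in SAP section 8. With 23 all-comers actually treated, the projected treated total is 25 + 23 + 20 = 68. At 125 mg it is 7 + 23 + 20 = 50.

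**What a pooled curve shows.** The documents give no liver data, so the values here are assumptions. Let N − 1 patients sit at b x ULN and one at p x ULN, all contributing to the same visit. The mean is ((N − 1)b + p)/N; the median stays at b.

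| N | b | p | Mean (x ULN) | Median (x ULN) |
|---|---|---|---|---|
| 68 | 0.5 | 3 | (67 × 0.5 + 3)/68 = 0.54 | 0.50 |
| 68 | 0.5 | 8 | (67 × 0.5 + 8)/68 = 0.61 | 0.50 |
| 68 | 0.5 | 20 | (67 × 0.5 + 20)/68 = 0.79 | 0.50 |
| 68 | 1.0 | 3 | (67 × 1.0 + 3)/68 = 1.03 | 1.00 |
| 68 | 1.0 | 20 | (67 × 1.0 + 20)/68 = 1.28 | 1.00 |
| 50 | 0.5 | 8 | (49 × 0.5 + 8)/50 = 0.65 | 0.50 |
| 20 | 0.5 | 8 | (19 × 0.5 + 8)/20 = 0.88 | 0.50 |

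The median never moves. At N = 68 the mean moves by at most about 0.3x ULN, even for a 20x peak.

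**What two separate shift tables show.** If a patients are high on ALT and c are high on bilirubin, the number high on both lies between max(0, a + c − N) and min(a, c).

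- a = 3, c = 3, N = 68: from 0 to 3.
- a = 10, c = 8, N = 68: from 0 to 8.

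The tables cannot narrow these ranges.

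**What reference-range categories show.** Suppose the categories are low, normal and high, which the SAP does not state. A patient may enter with ALT at 2x ULN, since 2 is below the 2.5x limit. A rise to 10x is then recorded as high to high, in the same cell as a patient who stays at 2x.

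**Joint output.** The SAP index (13.2) and the text of 11.5 and 11.5.6 contain no table, figure or listing that pairs transaminases with bilirubin, and no liver output specified in multiples of ULN.

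**The case against.** A reader might infer that a combined case would be averaged away and vanish from the report. The documents do not support that. The shift tables use each patient's worst post-baseline value and are split by cohort and dose level. The visit tables are also split by dose and carry a maximum, so pooling over doses applies, on the natural reading of their titles, only to the figures. Clinically significant abnormalities are adverse events and are graded, with tables and listings for Grade 3 or higher, dose-limiting toxicity and death. Listing 4.13 holds every value. Nor can one say that the liver figures are only averages: Figures 11, 12, 19 and 20 may be individual profiles. In a small group the gap between mean and median (0.88x against 0.50x at N = 20) would itself hint at an outlier. All of this stands.

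It does not close the gap. Every one of these laboratory tables and figures treats one test at a time. The adverse event route depends on judgement, because chemistry values judged not clinically significant are not entered as events (Protocol 7.6.1). The listing leaves the pairing to the reader, across about 68 patients and many visits.

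Two further objections are fair. SAP 13.1 says the index gives only a general idea of the output, so an unlisted display could still be produced; but neither the text nor the index commits to one. And any cut-off for a joint category is a choice the documents do not make, which could flag patients who entered with raised values. That is a reason to show baseline, and to treat cut-offs as display thresholds only.

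**Conclusion.** The point holds in limited form. For a named risk, the plan has no per-patient summary of combined transaminase and bilirubin elevation, and no liver output is specified in multiples of the local ULN. The mean and median curves cannot show an individual case. The worst-value shift tables can show that each test was high but not that both were high in the same patient. If their categories are low, normal and high, they also cannot show how large a rise was in a patient already above normal at entry. The information is collected and listed, so the weakness is in presentation, not loss of data. The sizes above rest on assumed liver values and on all patients contributing to one visit. The absence of a joint output rests on the SAP text and index alone. It is a worthwhile, inexpensive improvement and does not undermine the study.

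**What to change.** In SAP 11.5.6 and 13.2:

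- Express ALT, AST, ALP and bilirubin as multiples of the local ULN, using the reference ranges already obtained from sites.
- Add one table by cohort, dose level and overall, counting patients by category of peak post-baseline ALT or AST and of peak total bilirubin, separately and jointly, with baseline category and ALP shown. The sponsor sets the cut-offs (for example ALT or AST above 3x with bilirubin above 2x ULN) as display thresholds, not clinical rules. State the time window within which two peaks count as paired.
- Add a scatter plot of peak ALT or AST against peak total bilirubin in multiples of ULN, marked by dose, and a listing of patients in the joint category.
- Show the liver figures in multiples of ULN by dose level, state what Figures 11, 12, 19 and 20 display, and define the shift-table categories.

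The cost is a little extra programming; no new data are needed. Some patients may fall in the joint category because of raised baseline values or disease, which is why baseline belongs in the table. If the SAP can no longer be changed, Protocol 8.4 allows deviations from the planned analyses to be justified and presented in the study report.
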